6 STATISTICAL ANALYSIS

6.1. General Analysis Considerations

The statistical analyses will be reported using summary tables, listings, and figures (TFLs). Unless otherwise noted, all statistical testing will be 2-sided and will be performed at the 0.05 significance level. Tests will be declared statistically significant if the calculated P value is <0.05 .

Continuous variables will be summarized by presenting the number of observations, mean, standard deviation. Other summaries (e.g., 95% confidence interval [CI]) may be used as appropriate. Categorical variables will be summarized by presenting counts and percentages of patients in corresponding categories. Footnotes in the table will specify the percent basis in those cases.

All summary tables will be presented by treatment group. PK/PD data, and any derived data will be presented by patient in data listings.

The analyses described in this plan are considered a priori, in that they have been defined before unblinding.

[figure not shown]
All analyses and tabulations will be performed using R (version 4.0.1 or higher) or SAS (Version 9.4 or higher).

All analyses will be conducted by a designated statistician. The programming code, results, analysis report will be independently reviewed by another statistician.

[figure not shown]

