6.4. Statistical Analysis of Biomarker Data

For each marker, raw signal value, change from baseline, and percentage change from baseline will be analyzed. Summary statistics (for raw signal measurements, change from baseline, and percentage change from baseline) will be reported for each marker at baseline, Day 7, and Day 14 by treatment group.

Line plots of change and percentage change from baseline will be presented for each marker. Each line illustrates the value of a PD marker (Y-axis) changes over time (X-axis) of a single subject. Each marker will be represented by one line plot, in which all the subjects are included, treatment groups will be labelled by different colors. In addition, mean +/- stderr line plots will be generated for the two treatment groups.

For pRIP1 and pMLKL, similar line plots will be presented for pre-dose and post-dose separately. Specifically, Day 1 pre-dose and Day 1 post-dose values will be used, respectively, as the baseline for the calculation of the change from baseline for pre-dose and post-dose plots.

One-sample t-test will be used to evaluate if the change from baseline (Day 7 and Day 14 respectively) is significant (i.e., if the change is different from zero). This will be performed for each treatment group separately. Two-sample t-test will be performed to evaluate if the change is different between the two treatment groups. Test will not be performed on percentage change.

Boxplots will be used to graphically represent the data in the 1-sample and 2-sample tests, the test p-value will be displayed in the boxplots.

Heatmap will be used to visualize the percent change of the all the markers (by marker types) for all the subjects.

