7.1.2.2. T-test Results

Table 7.1.2.2.2. Changes on Biomarker Levels by Treatment Groups

Biomarker	Parameters	P value within Control	P value within Treatment	P value between Treatments
TNF-α	Change from Baseline to D7			
	Change from Baseline to D14			
INF-γ	Change from Baseline to D7			
	Change from Baseline to D14			
IL-1β	Change from Baseline to D7			
	Change from Baseline to D14			
IL-6	Change from Baseline to D7			
	Change from Baseline to D14			
IL-7	Change from Baseline to D7			
	Change from Baseline to D14			
IL-8	Change from Baseline to D7			
	Change from Baseline to D14			
IL-9	Change from Baseline to D7			
	Change from Baseline to D14			
IL-10	Change from Baseline to D7			
	Change from Baseline to D14			
IL-18				

Biomarker	Parameters	P value within Control	P value within Treatment	P value between Treatments
	Change from Baseline to D7			
	Change from Baseline to D14			
G-CSF				
	Change from Baseline to D7			
	Change from Baseline to D14			
GM-CSF				
	Change from Baseline to D7			
	Change from Baseline to D14			
CXCL-1				
	Change from Baseline to D7			
	Change from Baseline to D14			
CXCL-9				
	Change from Baseline to D7			
	Change from Baseline to D14			
CXCL-10				
	Change from Baseline to D7			
	Change from Baseline to D14			
MCP-1				
	Change from Baseline to D7			
	Change from Baseline to D14			
MIP-1α				
	Change from Baseline to D7			
	Change from Baseline to D14			
MIP-1β				
	Change from Baseline to D7			
	Change from Baseline to D14			
vWF				
	Change from Baseline to D7			

[figure not shown]
Biomarker	Parameters	P value within Control	P value within Treatment	P value between Treatments
Change from Baseline to D14				
P-Selectin				
	Change from Baseline to D7			
	Change from Baseline to D14			
Thrombomodulin				
	Change from Baseline to D7			
	Change from Baseline to D14			
NGAL				
	Change from Baseline to D7			
	Change from Baseline to D14			
KIM-1				
	Change from Baseline to D7			
	Change from Baseline to D14			
PBMC pRIP1 (Predose)				
	Change from Baseline to D7			
	Change from Baseline to D14			
PBMC pRIP1 (Post-dose)				
	Change from Baseline to D7			
	Change from Baseline to D14			
PBMC pMLKL (Predose)				
	Change from Baseline to D7			
	Change from Baseline to D14			
PBMC pMLKL (Post-dose)				
	Change from Baseline to D7			
	Change from Baseline to D14			
plasma pRIP1 (Predose)				
	Change from Baseline to D7			
	Change from Baseline to D14			

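### The PK/PD plan has a valid between-arm biomarker test, but leaves it unadjusted for baseline and surrounds it with 120 within-arm p-values that do not measure a drug effect

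*SAP*

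**What the plan says.** Section 6.4 of the PK/PD analysis plan sets two kinds of test on change from baseline. The first is within arm: "One-sample t-test will be used to evaluate if the change from baseline (Day 7 and Day 14 respectively) is significant", and "This will be performed for each treatment group separately". The second is between arms: "Two-sample t-test will be performed to evaluate if the change is different between the two treatment groups". Boxplots represent both kinds, and "the test p-value will be displayed in the boxplots".

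Section 6.1 applies one general rule: "all statistical testing will be 2-sided and will be performed at the 0.05 significance level", and "Tests will be declared statistically significant if the calculated P value is <0.05". It makes no exception for the within-arm tests.

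The t-test table shell in section 7.1.2.2 has a Day 7 and a Day 14 line for each marker and three p-value columns: within control, within treatment ("P value within Treatment") and between treatments. It shows no estimates or confidence intervals. The summary-statistics shell in section 7.1.2.1 shows no between-arm difference and no interval.

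For CRP, which is not one of these markers, protocol section 10.3.3 and SAP section 14.1.1 plan an ANCOVA with treatment and the baseline value, on the log scale, with 95% CIs within and between arms.

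**The concern.** The biomarker objectives ask what SIR1-365 does to these markers. The patients are hospitalised with severe disease and all receive standard care, so inflammatory and injury markers can move in both arms whatever the drug does. A test of zero change in the active arm cannot separate the drug from recovery or background treatment.

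Two of the three columns in the t-test table carry such tests. With control and treatment p-values side by side, a significant result on drug next to a non-significant one on placebo is easily taken for a drug effect, even though no test of the difference supports it. The protocol (section 10.1) intends this study's biomarker estimates for planning future studies, so a misreading could carry forward.

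The between-arm test that does answer the question is a t-test on raw change. It does not use the baseline value as a covariate, although the sponsor uses that method for CRP.

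**Working it through.** **Inputs.** About 30 patients per group, 60 in total (protocol 10.1, stated as not based on statistical significance). Two-sided 0.05 (PK/PD plan 6.1). Marker entries counted from the t-test shell (7.1.2.2). The common standardised change d, meaning mean change divided by the SD of change, is an assumption: the documents give no marker SDs, so a range is shown. There is no stated power or error rate to reproduce; the group sizes agree (2 × 30 = 60).

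**1. Count.** 11 cytokines + 6 chemokines + 3 endothelial + 2 kidney + 8 pRIP1/pMLKL (2 markers × plasma or PBMC × pre- or post-dose) = 30 entries.
- Within arm: 30 × 2 days × 2 arms = 120 p-values, 60 of them in the active arm.
- Between arms: 30 × 2 days = 60 p-values.

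**2. Active-only results without a drug effect.** Let p be the rejection rate of the one-sample t-test: non-central t with 29 degrees of freedom and non-centrality d√30. The arms are independent, so with the same d in both:
- P(significant on drug, not on placebo) = p(1−p)
- P(arms disagree) = 2p(1−p)

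| d | p | p(1−p) | 2p(1−p) | expected active-only lines of 60 |
|---|---|---|---|---|
| 0 | 0.050 | 0.048 | 0.095 | 2.8 |
| 0.2 | 0.185 | 0.151 | 0.302 | 9.1 |
| 0.37 | 0.500 | 0.250 | 0.500 | 15.0 |
| 0.5 | 0.754 | 0.186 | 0.371 | 11.1 |
| 0.8 | 0.988 | 0.011 | 0.023 | 0.7 |

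The last column takes the same d for every line. The maximum of p(1−p) is 0.25, at p = 0.5. With 20 or 15 patients per arm (possible for PBMC markers, prepared only at equipped sites), that maximum moves to d = 0.46 or 0.54.

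**3. Large common change.** At d = 0.8 active-only lines nearly vanish, but the active arm is significant in 98.8% of lines with no drug effect.

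**4. No change in either arm.** Expected significant active-arm tests: 60 × 0.05 = 3. P(at least one) = 1 − 0.95^60 = 95.4% if the tests are independent, and by simulation about 86% or 54% if they are correlated at 0.3 or 0.6.

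**5. Between-arm test under the same conditions.** In simulation (40,000 runs per value of d, from 0 to 0.8) the two-sample test rejected in 4.8% to 5.1% of runs, so it holds its level. At d = 0.37, only about 10% of active-only lines also had a significant between-arm test.

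**6. Baseline adjustment.** With equal SD σ at baseline and follow-up and correlation ρ, a change score has variance 2σ²(1−ρ). After ANCOVA adjustment the variance is σ²(1−ρ²). The ratio is (1−ρ²) / [2(1−ρ)] = (1+ρ)/2, which is below 1 for any ρ below 1 (ignoring the small cost of estimating the slope). The documents give no ρ, so the gain in precision cannot be stated as a number.

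**7. Post-dose pRIP1 and pMLKL.** For the post-dose plots, section 6.4 takes the Day 1 post-dose value as baseline. That sample is drawn 2 hours after the first dose, and the protocol (section 2.4) puts peak exposure at about 1 to 2 hours. It is therefore measured after treatment starts and may already carry a drug effect.

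**The case against.** The strongest reply is that the right comparison is already planned. The two-sample test follows directly in section 6.4, and its p-value stands on every line of the t-test table. That is correct. A reader might infer that the plan lacks a randomised comparison, or that it will claim a drug effect from the active-arm p-value. The documents support neither reading: section 6.4 says the one-sample test asks only whether change differs from zero, and nothing makes the active-only pattern a criterion. What stands is that the plan calls any p below 0.05 significant, does not mark the within-arm tests as descriptive, and does not say which result carries a treatment statement.

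A reader might also take 25% as the usual rate. It is the maximum. A large common change, which recovery and standard care could produce, takes it to about 1%.

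Nor does entry selection on CRP prove that these markers regress to the mean. CRP is not among the 30, and the effect on the others depends on correlations that the documents do not give.

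Replacing within-arm p-values by within-arm 95% CIs does not by itself remove the problem: a t-based interval excludes zero exactly when the one-sample p is below 0.05. This objection stands, so the intervals need a descriptive label and an explicit rule for treatment statements.

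Finally, this is an exploratory phase 1b study with a safety primary outcome, and the protocol offers p-values to aid interpretation. That limits the weight of the point but does not make the within-arm tests informative about the drug.

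**Conclusion.** The point holds as a reporting and precision matter for secondary biomarkers. The plan's between-arm test is valid but not adjusted for baseline. It is accompanied by twice as many within-arm p-values (120 against 60), which do not measure a drug effect and are not labelled descriptive. With equal change in both arms and 30 per arm, the chance per marker-time line of significance on drug only is about 5% at d = 0, 15% at 0.2, at most 25% at 0.37, 19% at 0.5 and 1% at 0.8. These figures assume the same d in both arms, normal data and complete groups of 30.

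The primary safety analysis and the CRP analyses are not touched.

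**What to change.** In the PK/PD plan, before unblinding:

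- Delete the one-sample t-tests from section 6.4, the two within-arm p-value columns from the table in 7.1.2.2, and the one-sample p-values from the boxplots.
- Report within-arm mean change with 95% CI, labelled descriptive. State in one sentence that treatment-effect statements rest only on the between-arm difference.
- Replace the two-sample t-test by an ANCOVA with treatment and the baseline marker value, and report the between-arm difference with 95% CI and p-value, following the CRP model. Whether to log-transform is a separate decision, because values below quantitation are set to 0 (section 6.2).
- For post-dose pRIP1 and pMLKL, use the Day 1 pre-dose value as covariate, and analyse the Day 7 or Day 14 post-dose value itself or its change from Day 1 pre-dose.

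The cost is plan wording, simpler table and figure shells, and a standard model; no new data are needed. The change leaves 60 between-arm tests without multiplicity adjustment, so about 3 (60 × 0.05) would still fall below 0.05 by chance if the drug had no effect. The report should say so.

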7 APPENDIX: TFL SHELLS

This section describes the shells for tables, listings, and figures.

List of TFLs

Table	
Number	Title
7.1.1.	PK Data
7.1.1.1.	Summary Statistics for Plasma Drug Level Data
7.1.2.	PD Data
7.1.2.1.	Summary Statistics
7.1.2.1.1.	Summary Statistics for Biomarker IL-6
7.1.2.1.2.	Summary Statistics for Biomarker TNF- α
7.1.2.1.3.	Summary Statistics for Biomarker IL-1 β
7.1.2.1.4.	Summary Statistics for Biomarker IL-8
7.1.2.1.5.	Summary Statistics for Biomarker IL-10

7.1.2.1.6.	Summary Statistics for Biomarker INF- γ
7.1.2.1.7.	Summary Statistics for Biomarker IL-7
7.1.2.1.8.	Summary Statistics for Biomarker GM-CSF
7.1.2.1.9.	Summary Statistics for Biomarker IL-9
7.1.2.1.10.	Summary Statistics for Biomarker IL-18
7.1.2.1.11.	Summary Statistics for Biomarker G-CSF
7.1.2.1.12.	Summary Statistics for Biomarker CXCL-1
7.1.2.1.13.	Summary Statistics for Biomarker CXCL-9
7.1.2.1.14.	Summary Statistics for Biomarker CXCL-10
7.1.2.1.15.	Summary Statistics for Biomarker MCP-1
7.1.2.1.16.	Summary Statistics for Biomarker MIP-1 α
7.1.2.1.17.	Summary Statistics for Biomarker MIP-1 β
7.1.2.1.18.	Summary Statistics for Biomarker Thrombomodulin
7.1.2.1.19.	Summary Statistics for Biomarker P-Selectin
7.1.2.1.20.	Summary Statistics for Biomarker vWF
7.1.2.1.21.	Summary Statistics for Biomarker KIM-1
7.1.2.1.22.	Summary Statistics for Biomarker NGAL
7.1.2.1.23.	Summary Statistics for Biomarker plasma pRIP1 (Predose)
7.1.2.1.24.	Summary Statistics for Biomarker plasma pRIP1 (Post-dose)
7.1.2.1.25.	Summary Statistics for Biomarker plasma pMLKL (Predose)
7.1.2.1.26.	Summary Statistics for Biomarker plasma pMLKL (Post-dose)
7.1.2.1.27.	Summary Statistics for Biomarker PBMC pRIP1 (Predose)
7.1.2.1.28.	Summary Statistics for Biomarker PBMC pRIP1 (Post-dose)
7.1.2.1.29.	Summary Statistics for Biomarker PBMC pMLKL (Predose)
7.1.2.1.30.	Summary Statistics for Biomarker PBMC pMLKL (Post-dose)
7.1.2.2.	T-test Results
7.1.2.2.1	Changes on Biomarker Levels by Treatment Groups

Figure	
Number	Title
7.2.1.	PK Data
7.2.1.1.	Mean Plasma Drug Levels Over Time by Treatment Group
7.2.2.	PD Data
7.2.2.1.1.	Individual Line Plot for IL-6
7.2.2.1.2.	Individual Line Plot for TNF- α
7.2.2.1.3.	Individual Line Plot for IL-1 β
7.2.2.1.4.	Individual Line Plot for IL-8
7.2.2.1.5.	Individual Line Plot for IL-10
7.2.2.1.6.	Individual Line Plot for INF- γ
7.2.2.1.7.	Individual Line Plot for IL-7
7.2.2.1.8.	Individual Line Plot for GM-CSF
7.2.2.1.9.	Individual Line Plot for IL-9
7.2.2.1.10.	Individual Line Plot for IL-18
7.2.2.1.11.	Individual Line Plot for G-CSF
7.2.2.1.12.	Individual Line Plot for CXCL-1
7.2.2.1.13.	Individual Line Plot for CXCL-9
7.2.2.1.14.	Individual Line Plot for CXCL-10
7.2.2.1.15.	Individual Line Plot for MCP-1
7.2.2.1.16.	Individual Line Plot for MIP-1 α
7.2.2.1.17.	Individual Line Plot for MIP-1 β
7.2.2.1.18.	Individual Line Plot for Thrombomodulin

7.2.2.1.19.	Individual Line Plot for P-Selectin
7.2.2.1.20.	Individual Line Plot for vWF
7.2.2.1.21.	Individual Line Plot for KIM-1
7.2.2.1.22.	Individual Line Plot for NGAL
7.2.2.1.23.	Individual Line Plot for plasma pRIP1 (Predose)
7.2.2.1.24.	Individual Line Plot for plasma pRIP1 (Post-dose)
7.2.2.1.25.	Individual Line Plot for plasma pMLKL (Predose)
7.2.2.1.26.	Individual Line Plot for plasma pMLKL (Post-dose)
7.2.2.1.27.	Individual Line Plot for PBMC pRIP1 (Predose)
7.2.2.1.28.	Individual Line Plot for PBMC pRIP1 (Post-dose)
7.2.2.1.29.	Individual Line Plot for PBMC pMLKL (Predose)
7.2.2.1.30.	Individual Line Plot for PBMC pMLKL (Post-dose)
7.2.2.2.1.	Mean IL-6 Levels Over Time by Treatment Group
7.2.2.2.2.	Mean TNF- α Levels Over Time by Treatment Group
7.2.2.2.3.	Mean IL-1 β Levels Over Time by Treatment Group
7.2.2.2.4.	Mean IL-8 Levels Over Time by Treatment Group
7.2.2.2.5.	Mean IL-10 Levels Over Time by Treatment Group
7.2.2.2.6.	Mean INF- γ Levels Over Time by Treatment Group
7.2.2.2.7.	Mean IL-7 Levels Over Time by Treatment Group
7.2.2.2.8.	Mean GM-CSF Levels Over Time by Treatment Group
7.2.2.2.9.	Mean IL-9 Levels Over Time by Treatment Group
7.2.2.2.10.	Mean IL-18 Levels Over Time by Treatment Group
7.2.2.2.11.	Mean G-CSF Levels Over Time by Treatment Group
7.2.2.2.12.	Mean CXCL-1 Levels Over Time by Treatment Group
7.2.2.2.13.	Mean CXCL-9 Levels Over Time by Treatment Group
7.2.2.2.14.	Mean CXCL-10 Levels Over Time by Treatment Group
7.2.2.2.15.	Mean MCP-1 Levels Over Time by Treatment Group
7.2.2.2.16.	Mean MIP-1 α Levels Over Time by Treatment Group
7.2.2.2.17.	Mean MIP-1 β Levels Over Time by Treatment Group
7.2.2.2.18.	Mean Thrombomodulin Levels Over Time by Treatment Group
7.2.2.2.19.	Mean P-Selectin Levels Over Time by Treatment Group
7.2.2.2.20.	Mean vWF Levels Over Time by Treatment Group
7.2.2.2.21.	Mean KIM-1 Levels Over Time by Treatment Group
7.2.2.2.22.	Mean NGAL Levels Over Time by Treatment Group
7.2.2.2.23.	Mean plasma pRIP1 Levels Over Time by Treatment Group
7.2.2.2.24.	Mean plasma pMLKL Levels Over Time by Treatment Group
7.2.2.2.25.	Mean PBMC pRIP1 Levels Over Time by Treatment Group
7.2.2.2.26.	Mean PBMC pMLKL Levels Over Time by Treatment Group
7.2.2.3.1.	Mean Changes from Baseline Over Time on IL-6 Levels by Treatment Group
7.2.2.3.2.	Mean Changes from Baseline Over Time on TNF- α Levels by Treatment Group
7.2.2.3.3.	Mean Changes from Baseline Over Time on IL-1 β Levels by Treatment Group
7.2.2.3.4.	Mean Changes from Baseline Over Time on IL-8 Levels by Treatment Group
7.2.2.3.5.	Mean Changes from Baseline Over Time on IL-10 Levels by Treatment Group
7.2.2.3.6.	Mean Changes from Baseline Over Time on INF- γ Levels by Treatment Group
7.2.2.3.7.	Mean Changes from Baseline Over Time on IL-7 Levels by Treatment Group
7.2.2.3.8.	Mean Changes from Baseline Over Time on GM-CSF Levels by Treatment Group
7.2.2.3.9.	Mean Changes from Baseline Over Time on L-9 Levels by Treatment Group

7.2.2.3.10.	Mean Changes from Baseline Over Time on IL-18 Levels by Treatment Group
7.2.2.3.11.	Mean Changes from Baseline Over Time on G-CSF Levels by Treatment Group
7.2.2.3.12.	Mean Changes from Baseline Over Time on CXCL-1 Levels by Treatment Group
7.2.2.3.13.	Mean Changes from Baseline Over Time on CXCL-9 Levels by Treatment Group
7.2.2.3.14.	Mean Changes from Baseline Over Time on CXCL-10 Levels by Treatment Group
7.2.2.3.15.	Mean Changes from Baseline Over Time on MCP-1 Levels by Treatment Group
7.2.2.3.16.	Mean Changes from Baseline Over Time on MIP-1 α Levels by Treatment Group
7.2.2.3.17.	Mean Changes from Baseline Over Time on MIP-1 β Levels by Treatment Group
7.2.2.3.18.	Mean Changes from Baseline Over Time on Thrombomodulin Levels by Treatment Group
7.2.2.3.19.	Mean Changes from Baseline Over Time on P-Selectin Levels by Treatment Group
7.2.2.3.20.	Mean Changes from Baseline Over Time on vWF Levels by Treatment Group
7.2.2.3.21.	Mean Changes from Baseline Over Time on KIM-1 Levels by Treatment Group
7.2.2.3.22.	Mean Changes from Baseline Over Time on NGAL Levels by Treatment Group
7.2.2.3.23.	Mean Changes from Baseline Over Time on plasma pRIP1 Levels by Treatment Group
7.2.2.3.24.	Mean Changes from Baseline Over Time on plasma pMLKL Levels by Treatment Group
7.2.2.3.25.	Mean Changes from Baseline Over Time on PBMC pRIP1 Levels by Treatment Group
7.2.2.3.26.	Mean Changes from Baseline Over Time on PBMC pMLKL Levels by Treatment Group
7.2.2.4.1.	Mean Percentage Changes from Baseline Over Time on IL-6 Levels by Treatment Group
7.2.2.4.2.	Mean Percentage Changes from Baseline Over Time on TNF- α Levels by Treatment Group
7.2.2.4.3.	Mean Percentage Changes from Baseline Over Time on IL-1 β Levels by Treatment Group
7.2.2.4.4.	Mean Percentage Changes from Baseline Over Time on IL-8 Levels by Treatment Group
7.2.2.4.5.	Mean Percentage Changes from Baseline Over Time on IL-10 Levels by Treatment Group
7.2.2.4.6.	Mean Percentage Changes from Baseline Over Time on INF- γ Levels by Treatment Group
7.2.2.4.7.	Mean Percentage Changes from Baseline Over Time on IL-7 Levels by Treatment Group
7.2.2.4.8.	Mean Percentage Changes from Baseline Over Time on GM-CSF Levels by Treatment Group
7.2.2.4.9.	Mean Percentage Changes from Baseline Over Time on IL-9 Levels by Treatment Group
7.2.2.4.10.	Mean Percentage Changes from Baseline Over Time on IL-18 Levels by Treatment Group

7.2.2.4.11.	Mean Percentage Changes from Baseline Over Time on G-CSF Levels by Treatment Group
7.2.2.4.12.	Mean Percentage Changes from Baseline Over Time on CXCL-1 Levels by Treatment Group
7.2.2.4.13.	Mean Percentage Changes from Baseline Over Time on CXCL-9 Levels by Treatment Group
7.2.2.4.14.	Mean Percentage Changes from Baseline Over Time on CXCL-10 Levels by Treatment Group
7.2.2.4.15.	Mean Percentage Changes from Baseline Over Time on MCP-1 Levels by Treatment Group
7.2.2.4.16.	Mean Percentage Changes from Baseline Over Time on MIP-1 α Levels by Treatment Group
7.2.2.4.17.	Mean Percentage Changes from Baseline Over Time on MIP-1 β Levels by Treatment Group
7.2.2.4.18.	Mean Percentage Changes from Baseline Over Time on Thrombomodulin Levels by Treatment Group
7.2.2.4.19.	Mean Percentage Changes from Baseline Over Time on P-Selectin Levels by Treatment Group
7.2.2.4.20.	Mean Percentage Changes from Baseline Over Time on vWF Levels by Treatment Group
7.2.2.4.21.	Mean Percentage Changes from Baseline Over Time on KIM-1 Levels by Treatment Group
7.2.2.4.22.	Mean Percentage Changes from Baseline Over Time on NGAL Levels by Treatment Group
7.2.2.4.23.	Mean Percentage Changes from Baseline Over Time on plasma pRIP1 Levels by Treatment Group
7.2.2.4.24.	Mean Percentage Changes from Baseline Over Time on plasma pMLKL Levels by Treatment Group
7.2.2.4.25.	Mean Percentage Changes from Baseline Over Time on PBMC pRIP1 Levels by Treatment Group
7.2.2.4.26.	Mean Percentage Changes from Baseline Over Time on PBMC pMLKL Levels by Treatment Group
7.2.2.5.1.	Boxplot of Changes from Baseline on IL-6 by Treatment Group
7.2.2.5.2.	Boxplot of Changes from Baseline on TNF- α by Treatment Group
7.2.2.5.3.	Boxplot of Changes from Baseline on IL-1 β by Treatment Group
7.2.2.5.4.	Boxplot of Changes from Baseline on IL-8 by Treatment Group
7.2.2.5.5.	Boxplot of Changes from Baseline on IL-10 by Treatment Group
7.2.2.5.6.	Boxplot of Changes from Baseline on INF- γ by Treatment Group
7.2.2.5.7.	Boxplot of Changes from Baseline on IL-7 by Treatment Group
7.2.2.5.8.	Boxplot of Changes from Baseline on GM-CSF by Treatment Group
7.2.2.5.9	Boxplot of Changes from Baseline on IL-9 by Treatment Group
7.2.2.5.10.	Boxplot of Changes from Baseline on IL-18 by Treatment Group
7.2.2.5.11.	Boxplot of Changes from Baseline on G-CSF by Treatment Group
7.2.2.5.12.	Boxplot of Changes from Baseline on CXCL-1 by Treatment Group
7.2.2.5.13.	Boxplot of Changes from Baseline on CXCL-9 by Treatment Group
7.2.2.5.14.	Boxplot of Changes from Baseline on CXCL-10 by Treatment Group
7.2.2.5.15.	Boxplot of Changes from Baseline on MCP-1 by Treatment Group
7.2.2.5.16.	Boxplot of Changes from Baseline on MIP-1 α by Treatment Group
7.2.2.5.17.	Boxplot of Changes from Baseline on MIP-1 β by Treatment Group
7.2.2.5.18.	Boxplot of Changes from Baseline on Thrombomodulin by Treatment Group
7.2.2.5.19.	Boxplot of Changes from Baseline on P-Selectin by Treatment Group
7.2.2.5.20.	Boxplot of Changes from Baseline on vWF by Treatment Group
7.2.2.5.21.	Boxplot of Changes from Baseline on KIM-1 by Treatment Group

7.2.2.5.22.	Boxplot of Changes from Baseline on NGAL by Treatment Group
7.2.2.5.23.	Boxplot of Changes from Baseline on plasma pRIP1 by Treatment Group
7.2.2.5.24.	Boxplot of Changes from Baseline on plasma pMLK by Treatment Group
7.2.2.5.25.	Boxplot of Changes from Baseline on PBMC pRIP1 by Treatment Group
7.2.2.5.26.	Boxplot of Changes from Baseline on PBMC pMLKL by Treatment Group
7.2.2.6.1.	Heatmap of Percentage Change from Baseline to D7 on Biomarkers Indicative of Inflammatory Biomarkers by Treatment Group
7.2.2.6.2.	Heatmap of Percentage Change from Baseline to D14 on Biomarkers Indicative of Inflammatory Biomarkers by Treatment Group
7.2.2.6.3.	Heatmap of Percentage Change from Baseline to D7 on Biomarkers Indicative of CV Endothelial Cell Damage by Treatment Group
7.2.2.6.4.	Heatmap of Percentage Change from Baseline to D14 on Biomarkers Indicative of CV Endothelial Cell Damage by Treatment Group
7.2.2.6.5.	Heatmap of Percentage Change from Baseline to D7 on Biomarkers Indicative of Kidney Injury by Treatment Group
7.2.2.6.6.	Heatmap of Percentage Change from Baseline to D14 on Biomarkers Indicative of Kidney Injury by Treatment Group
7.2.2.6.7.	Heatmap of Percentage Change from Baseline to D7 on Biomarkers Indicative of Target Engagement by Treatment Group
7.2.2.6.8.	Heatmap of Percentage Change from Baseline to D14 on Biomarkers Indicative of Target Engagement by Treatment Group

Listing	
Number	Title
7.3.1.	PK Data
7.3.2.	PD Data
7.3.2.1.	Listing for Biomarkers Indicative of Inflammation
7.3.2.2.	Listing for Biomarkers Indicative of CV Endothelial Cell Damage
7.3.2.3.	Listing for Biomarkers Indicative of Kidney Injury
7.3.2.4.	Listing for Biomarkers Indicative of Target Engagement

